6.4 Multiple Comparisons and Multiplicity

Planned adjustments for multiplicity are described in Section 9.2.

6.5 Significance Level

Unless otherwise noted, all statistical analyses will be conducted with a significance level (α) of 0.05 and utilize two-sided testing.

6.6 Statistical Notation and Methodology

Unless stated otherwise, the term “descriptive statistics” refers to the number of subjects (n), mean, median, standard deviation (SD), minimum (min), and maximum (max) for continuous data and frequencies and percentages for categorical data. Min and max values will be rounded to the precision of the original value, means and medians will be rounded to 1 decimal place greater than the precision of the original value, and SDs will be rounded to 2 decimal places greater than the precision of the original value. Percentages will be rounded to the nearest whole number (zeros are not displayed) with values of “ $< 1\%$ ” and “ $> 99\%$ ” shown as necessary for values falling near the boundaries. P-values will be presented with 3 decimal places and values less than 0.001 will be presented as < 0.001 .

Unless otherwise noted, all data collected during the study will be included in data listings and will be sorted by treatment arm, subject number and then by date/time for each subject.

7 DATA HANDLING METHODS

7.1 Missing Data

Every effort will be made to obtain the protocol-specified data for all study assessments at each scheduled visit for all subjects.

7.1.1 Date Values

In cases of incomplete dates (e.g., pertaining to AE, concomitant medication, medical history, etc.), the missing component(s) will be assumed as the most conservative value(s) possible, as follows. Date imputation will only be used for computational purposes, such as calculation of study day, determination of prior versus concomitant medications, and determination of treatment-emergent adverse events. Actual date values, as they appear in the original eCRFs, will be displayed in listings.

Date	Possible Date Range	Impute as...	Reason
Start Date	Definitely before date of procedure	Earliest possible date	Longest possible duration
Start Date	Before or after date of procedure, depending on imputation	Impute as earliest possible date, on or after date of procedure	Greatest potential causality
Start Date	Definitely after date of procedure	Earliest possible date	Longest possible duration
End Date	Any	Latest possible date	Longest possible duration

7.2 Imputation of AF/ AFL/AT Freedom

Subjects who were randomized and received study procedure but have no post-treatment assessments will be conservatively imputed as having failed to achieve freedom from AF/ AFL/AT (e.g., treatment failure). Similarly, subjects who were randomized and received study procedure but do not have treatment assessments following the 3-month blanking period (as described in Section 7.4.2), or a visit was performed but insufficient information was collected to determine whether or not AF/AFL/AT was experienced and/or whether Class I/III AADs were administered, will also be imputed as treatment failures. Subjects who do not have complete information for the efficacy evaluation period (for example, withdrew before 12 months) but have sufficient information to conclude that they would be classified as *not* AF/AFL/AT free (such as: new or increased dose of Class I/III AAD or documented findings of AF/AFL/AT) will be considered treatment failures. These subjects will *not* be considered to have been imputed, for the purpose of tipping point or multiple imputation analyses, as it is clear that they would have been treatment failures even if complete information had been collected.

The same approach will be utilized to impute AF freedom for secondary efficacy analyses.

A tipping-point analysis will also be performed, as described in Section 9.3.2, which will be performed on un-imputed data. Further details on criteria for treatment failure are provided in study protocol Section 1.5.

7.3 Visit Windows

All data will be listed according to the nominal visit obtained from the CRF. Visits will also be assigned an analysis visit, used for data summaries and analyses, based on visit

windowing.

Section 3.2 defines the tolerance range for each follow-up visit. A visit that occurs outside the specified range will be categorized as an unscheduled visit, and excluded from summaries and analyses. If an additional visit was not performed within that visit window, the visit will be identified as a protocol violation. That is, an unscheduled visit will be windowed to the nearest visit, but will not be considered a protocol deviation if the regularly scheduled visit occurred within its window.

If more than one visit falls within a given visit window for a subject:

- If only one visit has non-missing data, the data from the visit with non-missing data will be assigned to that analysis visit, and used for summaries and analyses.
- If >1 visit has non-missing data, the data from the latest visit within the window will be assigned to that analysis visit, and used for summaries and analyses.

7.4 Data Derivations and Definitions

The following definitions and derivations will be used for this study.

7.4.1 Baseline

The baseline value will be the last non-missing value collected before study treatment. This may be collected at the Baseline visit, Pre-Procedure visit, or an unscheduled visit.

Change from baseline will be calculated as observed value – baseline value. Percent change from baseline will be calculated as change from baseline divided by the baseline value, multiplied by 100.

7.4.2 Study Day, Blanking Period, and Time Points

Relevant assessments (e.g. Rhythm Disturbance Evaluation) which do not have a specific date on the CRF page will be assigned the date for that study visit. Inclusion of that assessment in the analyses of study endpoints will be based on whether that visit date falls within the efficacy evaluation window. Other assessments (ECG, Holter monitor, etc.) will be included or excluded based on the date recorded on the specific CRF page.

- Day 1 will be considered the date of study procedure. Study day will be computed as Date – Study Procedure Date + 1 for assessments or events on or after the date of procedure, and as Date – Study Procedure Date for assessments or events prior to the date of procedure.
- The 3 month blanking period is defined as the time from the date of study

procedure until 3 months post-procedure. If the subject's 3 month visit is within the visit window specified in Section 3.2 (90 days \pm 15 days), the day of the 3 month visit will be the last day of the blanking period. If the nominal 3 month visit is not performed but an unscheduled visit falls within that visit window and is categorized as the 3 month visit per Section 7.3, the day of that visit will be the last day of the blanking period. If multiple unscheduled visits fall within that window (and there is no nominal 3 month visit), the unscheduled visit (with sufficient efficacy data to determine if a subject was AT/AF/AFL free) closest to the 90 day mark will be used to determine the end of the blanking period. If a subject does not have a visit within the 3 month window, the blanking period will end on the 90th day after study procedure.

- Similarly, the 12 month post-procedure visit (as defined for the end of the efficacy evaluation period) will be determined as follows. If the subject's 12 month visit is within the visit window specified in Section 3.2 (365 days \pm 30 days), the day of the 12 month visit will be used. If the nominal 12 month visit is not performed but an unscheduled visit falls within that visit window and is categorized as the 12 month visit per Section 7.3, the day of that visit will be used. If multiple unscheduled visits fall within that window (and there is no nominal 12 month visit), the unscheduled visit closest (with sufficient efficacy data to determine if a subject was AT/AF/AFL free) to the 365 day mark will be considered the 12 month post-procedure visit for this purpose. If a subject does not have a visit within the 12 month window, but has subsequent study visits or other criteria such that it is necessary to define a date for the hypothetical 12 month visit, the 365th day after the study procedure will be used.
- If necessary, the 1 month visit, 6 month visit and 18 month long-term follow-up visit date will be defined as necessary for efficacy purposes using the approach spelled out for the 12 month visit.

7.4.3 **Anti-Arrhythmic Drugs**

Class I/III AADs will include Quinidine, Procainamide, Disopyramide, Lidocaine, Phenytoin, Mexiletine, Tocainide, Flecainide, Propafenone, and Moricizine (Class I AADs) as well as Amiodarone, Sotalol, Ibutilide, Dofetilide, Dronedarone, and E-4031 (Class III AADs). Prior to database lock, a list of all medications (both prior and concomitant) taken by subjects who have received a study procedure will be provided to the Medical Monitor or designee for review. This list will not include subject identifiers or treatment arm. The Medical Monitor or designee will indicate which medications should be categorized as Class I or III AADs. This information will be finalized prior to database lock and subsequent unblinding of study sponsor, and incorporated into analysis datasets. If desired, a list of previously failed Class I/III AADs as recorded at the Baseline visit may also be provided to the monitor or designee for reference.

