**6.6 Month 12 Visit (365 days +/- 30 days post index procedure)**

Subjects will return for a post-procedure follow up visit at 12 months to evaluate their progress. The 12 month post procedure assessment will include:

- ECG – subject rhythm evaluation
- 24 hour Holter monitor

- Evaluation of any adverse events
- Evaluation of any major adverse events (MAEs)
- Medications – class I and III AADs, other cardiac medications and anticoagulants
- Any AF treatment that was needed
- Quality of Life (QOL) assessments (SF36 and Univ. of Toronto)
- Six minute walk test
- Complete the subject study completion CRF
- Remind subject that he does have to come in for the long-term 18 month post procedure follow-up visit and participate in annual phone follow-ups at 2, 3, 4, 5 years post procedure.

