7.4.4 AF Freedom

A subject will be considered **AF free** for a time period if the subject:

- Does not exhibit AF
- Has sufficient efficacy assessments to determine that AF was not present
- Does not meet failure criteria (including the use of new Class I/III AADs or increased dose of a previously failed Class I/III AAD). Criteria for treatment failure is provided in the study protocol section 1.5.

If a subject exhibits AF or meets failure criteria, the subject will be classified as **not AF free** for that time period. If a subject has insufficient efficacy assessments and does not meet failure criteria, and does not exhibit AF on any efficacy assessments during that period, the subject will be classified as **indeterminate**, and subject to imputation as described in Sections 7.2 and 9.3.

Does not exhibit AF is defined as:

Subject has no atrial fibrillation, where atrial fibrillation is defined as a Holter monitor finding or ECG rhythm of 'AF' or 'Other' with description including atrial fibrillation, where the Holter monitor date or ECG date falls within that period. (Note that findings of AF/AFL/AT without specific information that AF is present will not be considered demonstration of AF).

A list of descriptions for 'Other' results from the Holter monitor and ECG will be tabulated and provided to the Medical Monitor or designee to determine whether the description is indicative of the subject having AF. This tabulation will not include subject identifiers or treatment arm. Additional information collected on the Holter monitor, ECG, or Rhythm Disturbance Evaluation eCRF from that visit may also be provided to help with classification. This information will be finalized prior to database lock and subsequent unblinding of study sponsor, and incorporated into analysis datasets in order to determine if subjects meet criteria for to be AF free at a given assessment, and hence determine if the subject is AF free for a given period of time.

Has sufficient efficacy assessments to determine that AF was not present is defined as:

A subject must have either Holter monitor, ECG, or Rhythm Disturbance Evaluation results indicating no AF at each scheduled visit within that period (for example, both 6 & 12 month visits, for the period after the blanking period through the 12 month visit), in order to be considered AF free for that period.

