If a subject exhibits AF, AFL, or AT or meets failure criteria, the subject will be classified as **not AF/AFL/AT free** for that time period. If a subject has insufficient efficacy assessments and does not meet failure criteria, and does not exhibit AF/AFL/AT on any efficacy assessments during that period, the subject will be classified as **indeterminate**, and subject to imputation as described in Sections 7.2 and 9.3. Further details on criteria for treatment failure are provided in study protocol section 1.5.

Does not exhibit AF, AFL, or AT is defined as:

- Has no atrial fibrillation, where atrial fibrillation is defined as a Holter monitor finding or ECG rhythm of 'AF' or 'Other' with description including atrial

fibrillation, where the Holter monitor date or ECG date falls within that period.

- Has no atrial flutter, where atrial flutter is defined as a Holter monitor finding or ECG rhythm of 'Typical AFL (Right Atrial)' or 'Atypical AFL (Left Atrial)' or 'Other' with description including atrial flutter, where the Holter monitor date or ECG date falls within that period.
- Has no atrial tachycardia, where atrial tachycardia is defined as a Holter monitor finding or ECG rhythm of 'AT' or 'Other' with description including atrial tachycardia, where the Holter monitor date or ECG date falls within that period.
- Has a Rhythm Disturbance Evaluation eCRF where 'any symptomatic AF/AFL/AT episodes' is marked No or Unknown at each visit where completed.
- Has a Holter monitor eCRF where the number of >30 second AF/AFL/AT episodes is 0 for each eCRF page where the Holter monitor date falls within that period.

A list of descriptions for 'Other' results from the Holter monitor and ECG will be tabulated and provided to the Medical Monitor or designee to determine whether the description is indicative of the subject having AF/AFL/AT. This tabulation will not include subject identifiers or treatment arm. Additional information collected on the Holter monitor, ECG, or Rhythm Disturbance Evaluation eCRF from that visit may also be provided to help with classification. This information will be finalized prior to database lock and subsequent unblinding of study sponsor, and incorporated into analysis datasets in order to determine if subjects meet criteria for to be AF/AFL/AT free at a given assessment, and hence determine if the subject is AF/AFL/AT free for a given period of time.

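### A 12-month Holter dated after the day of the 12-month visit falls outside the primary evaluation period, so AF/AFL/AT recorded on it does not count as failure

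*SAP*

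**What the plan says.** SAP 7.4.2 fixes the close of the primary evaluation period: "the 12 month post-procedure visit (as defined for the end of the efficacy evaluation period) will be determined as follows". If the visit falls within 365 ± 30 days, "the day of the 12 month visit will be used". The period therefore stops on the visit day, not at the end of the visit window.

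The same section treats two kinds of assessment differently. Those "which do not have a specific date on the CRF page will be assigned the date for that study visit". For the rest, "Other assessments (ECG, Holter monitor, etc.) will be included or excluded based on the date recorded on the specific CRF page".

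The endpoint definitions follow the date rule. In SAP 7.4.4 and 7.4.5 an arrhythmia finding counts only "where the Holter monitor date or ECG date falls within that period". SAP 7.4.5 adds that the "number of >30 second AF/AFL/AT episodes is 0 for each eCRF page where the Holter monitor date falls within that period". The sufficiency rule in 7.4.5 is met at each scheduled visit by any one of a Holter, an ECG or a Rhythm Disturbance Evaluation showing no arrhythmia; a 12-month Holter is not required.

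Protocol 6.6 lists a "24 hour Holter monitor" among the Month 12 assessments. Protocol 1.5.1 and SAP 2.3.1 make any Holter-documented episode of 30 seconds or longer, after blanking and through the 12-month visit, a primary failure.

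**The concern.** A Holter required for the 12-month visit can carry a later date than the visit. It may be fitted on another day, or a 24-hour recording started at the visit may be dated by its end. Under the rules above that recording is outside the period, and arrhythmia on it does not make the subject a failure.

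The 12-month Holter is one of only two Holters scheduled between the end of blanking and month 12, and the only one after month 6. Protocol 1.5.1 relies on independent review of Holter data to keep the endpoint objective in an open-label trial. No such review is stated for ECGs or for the Rhythm Disturbance form, whose symptom item passes in SAP 7.4.5 when marked No or Unknown. Where the Holter is dropped, the 12-month result rests on those weaker sources.

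**Working it through.** **Classification.** Let D be the day of an in-window 12-month visit. Suppose month 6 is clean, the ECG on day D shows no arrhythmia, no other failure criterion is met, and the 12-month Holter shows an AF episode of more than 30 seconds.

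| 12-month Holter | Date on CRF page | Inside period ending on D? | Result under SAP 7.4.5 |
|---|---|---|---|
| Fitted before D, dated on or before D | ≤ D | Yes | Failure |
| Fitted on D, dated by start | D | Yes | Failure |
| Fitted on D, dated by end of 24 h | D + 1 | No | AF/AFL/AT free |
| Fitted after D, dated by start or end | ≥ D + 1 | No | AF/AFL/AT free |

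In the last two rows the day-D ECG satisfies sufficiency, so the subject is neither failed nor indeterminate.

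**Would another analysis catch it?** SAP 7.2 imputes failure only where assessments are absent or insufficient. The tipping-point analysis (9.3.2) and multiple imputation (9.3.4) act on missing outcomes, and this outcome is recorded as observed. The mITT and PP repeats in 9.3.1 rerun the primary analysis and so carry the same classification.

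**Effect per subject.** With the planned 51 control and 102 convergent subjects (SAP 4):
- control: 1/51 = 1.96 points
- convergent: 1/102 = 0.98 points

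**The plan's sample size.** Inputs from SAP 4 are 40% against 65%, two-sided alpha 0.05, power 80%, 2:1 allocation and 10% dropout. With pooled proportion (0.40 + 2 × 0.65)/3 = 0.5667:

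n(control) = [1.960 × √(1.5 × 0.5667 × 0.4333) + 0.842 × √(0.40 × 0.60 + 0.65 × 0.35/2)]² / 0.25² = 45.7, rounded up to 46.

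That gives 46 + 92 = 138, and 138/0.90 = 153.3, which agrees with the stated 153 apart from rounding. Power at 46:92 is 80.3%.

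**Illustration under an assumption.** Let m be the share of true failures whose only failing evidence is a 12-month Holter dated after the visit. The documents give no value for m, so the range below is assumed. With the same m in both arms, observed success is 0.40 + 0.60m (control) and 0.65 + 0.35m (convergent), and the difference is 0.25(1 − m).

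| Assumed m | Control | Convergent | Difference | Power at 46:92 |
|---|---|---|---|---|
| 0 | 40.0% | 65.0% | 25.0 points | 80.3% |
| 5% | 43.0% | 66.75% | 23.75 points | 76.4% |
| 10% | 46.0% | 68.5% | 22.5 points | 72.4% |
| 20% | 52.0% | 72.0% | 20.0 points | 64.1% |

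Unequal shares move the difference either way. With m = 10% in the convergent arm only, it is 68.5 − 40.0 = 28.5 points. With m = 10% in the control arm only, it is 65.0 − 46.0 = 19.0 points. If instead the same number of percentage points is added to both arms, the difference stays at 25.

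**The case against.** The strongest reply is that the problem depends on a date convention the documents do not give. The SAP refers readers to the eCRFs for data-collection detail. If the Holter page records the start of recording and Holters are fitted at or before the visit, every 12-month Holter counts and nothing is lost. This stands as a limit on size: the effect could be nil. It does not cure the rule, because a Holter fitted after the visit is dropped under a start or an end date.

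The rule also applies identically to both arms. A reader might infer that it favours the convergent procedure. The documents do not support that: an equal share of missed failures shrinks the difference, and nothing shows that Holter timing differs by arm. Nor do they show that timing is balanced in this open-label trial.

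Two further inferences are tempting:

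- That one recording showing continuous AF could make a subject an AF-burden failure and a primary success. SAP 7.3 assigns visits, not individually dated Holters, to windows, and 9.4.1 gives no rule for a Holter dated after the visit, so the conflict is not stated. A subject in continuous AF would also probably show it on the visit-day ECG and fail there. The realistic exposure is intermittent arrhythmia or a Holter fitted on a later day.
- That the independently read part of the endpoint is lost. The 6-month Holter remains, as does every 12-month Holter dated on or before the visit.

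**Conclusion.** The point holds as a conditional misclassification written into the SAP. Whenever the 12-month Holter is dated after the day of an in-window visit, arrhythmia on it is disregarded, and one clean visit-day assessment can leave the subject an observed success. That contradicts a failure definition running through the 12-month visit, of which the protocol makes this Holter a part.

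The size per affected subject is about 2.0 points in control or 1.0 point in the convergent arm. The number affected and the direction of net bias cannot be obtained from the documents; the power figures above rest wholly on assumed values of m. The rule merits correction because it can misclassify the primary outcome, no planned missing-data analysis would reveal it, and the remedy is small.

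**What to change.** Keep the end of the period at the 12-month visit date for AAD use, cardioversion and ablation. Moving the end of the whole period would extend exposure to those criteria past the visit, beyond what the protocol defines.

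In SAP 7.4.2, 7.4.4 and 7.4.5, add that:

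- the protocol-required Holter and ECG performed for the 12-month visit count toward the primary and AF-freedom endpoints even if their CRF date is after the visit day, provided recording starts no later than 395 days post-procedure;
- the recording start date governs.

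The limit is 365 + 30 = 395 days. Because 7.4.2 makes the procedure date Day 1, that is Study Day 396. Applying it to the start of recording keeps a Holter fitted on the last in-window day.

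Use the same assignment for 12-month AF burden in 9.4.1, so that both endpoints use the same recording.

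The cost is a short SAP addition and one programming rule, settled before unblinding, plus a check of what the Holter page's date denotes. No new assessments are needed. Success rates may come out slightly lower in both arms.

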#### **6.1 Blanking Period**

The period from index procedure to the 3 month post procedure visit will be considered a blanking period. During the blanking period, the use of AADs, cardioversions, and any recurrence or episodes of AF will not be considered a treatment failure. Subjects who receive AF therapy (a new class I/III AAD, or an increase in dose of a previously failed class I/III AAD therapy, DCCV, pharmacological cardioversion, RFCA) following the 3 month blanking period through the 12 months post procedure follow-up visit will be considered primary efficacy failures. Subjects receiving RFCA for the treatment of AF, left-sided atypical atrial flutter, or atrial tachycardia at anytime (even within the blanking period) after the index procedure will be deemed primary efficacy failures; any RFCA should be performed in accordance with Attachment F – Repeat Catheter Ablation Protocol. Subjects in either arm of the study who are efficacy failures (documented by the 24 hour holter results), at the six month post procedure follow-up time point, may undergo an ablation procedure per physician recommendation. Subjects will be deemed efficacy failures, the ablation will be recorded as a rhythm disturbance treatment within the TEMPO EDC system, and the subjects will be continued to be monitored per protocol requirements.

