**6.4 Month 3 Visit (90 days +/- 15 days post index procedure)**

Subjects in both study arms will return for a post-procedure follow up visit at 3 months to evaluate their progress. The 3 month post procedure assessment will include:

- ECG – subject rhythm evaluation
- Evaluation of any adverse events
- Evaluation of any major adverse events (MAEs)
- Medications – Class I & III AADs, other cardiac medications and anticoagulants
- Subject should discontinue class I and III AADs if medically warranted (may alternatively continue previously failed class I or III AAD at pre-procedure dose or lower)
- Any AF treatment that was needed
- Schedule subject for 6 month visit with Holter monitor assessment
- Instruct subject to contact the site coordinator if they are experiencing any symptomatic atrial tachyarrhythmia episodes at anytime during the post 3 month blanking period/post-procedure follow-up visit through the 12 month post-procedure follow-up visit.

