#### **12.5 Visit Boundaries and Missed Visits**

Section 6.0 defines the tolerance range for each follow-up visit. A visit that occurs outside of the specified range will be coded using the closest follow-up window and identified as a protocol deviation on the study non-compliance log located within the site regulatory binder.

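### A 3-month visit later than 105 days after the procedure moves the end of blanking back to 90 days (SAP 7.4.2), so treatment events that Protocol 6.1 blanks become primary failures

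*SAP*

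**What the plan says.** All day counts here are days after the procedure. SAP study days are one higher, because SAP 7.4.2 calls the procedure date Day 1.

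- **Protocol 6.1:** "The period from index procedure to the 3 month post procedure visit will be considered a blanking period". AAD use, cardioversion and AF recurrence in that time are not failures (repeat ablation for AF or left-sided arrhythmia is treated separately).
- **Protocol 6.4:** the Month 3 visit is due at 90 days, plus or minus 15.
- **Protocol 12.5:** "A visit that occurs outside of the specified range will be coded using the closest follow-up window", and is logged as a deviation.
- **Protocol 6.0, 6.4 and Attachment D:** AAD weaning is tied to the 3-month visit.
- **SAP 3.2:** repeats the Protocol's definition of blanking and refers to SAP 7.4.2 for detail.
- **SAP 7.4.2:** for a visit inside the window, "the day of the 3 month visit will be the last day of the blanking period". An unscheduled visit in the window can take its place. With no visit in the window, "If a subject does not have a visit within the 3 month window, the blanking period will end on the 90th day after study procedure". On dating: "Other assessments (ECG, Holter monitor, etc.) will be included or excluded based on the date recorded on the specific CRF page". Undated forms, such as the Rhythm Disturbance Evaluation, take the visit date.
- **SAP 7.3:** an out-of-window visit is treated as unscheduled and left out of analyses. The same paragraph then assigns unscheduled visits to the nearest visit.
- **SAP 13:** lists several departures from the Protocol, including the wider definition of cardioversion, but not the 90-day default.

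**The concern.** The SAP rule steps backwards. Up to 105 days, a later visit means a longer blanking period. One day later, blanking ends at 90 days, and time that has already passed is reclassified as follow-up in which failure can occur.

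The events exposed are mainly treatment events with their own dates. Suppose a subject receives, during blanking, a Class I/III AAD that does not match a previously failed drug by name and dose, and stops it at the 3-month visit. If that visit is at 105 days, the use is blanked. If it is at 106 days, the use from day 91 on is a primary failure under SAP 7.4.5, with no rhythm recurrence needed. A cardioversion at 98 days is reclassified in the same way.

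The primary endpoint then depends in part on appointment timing. Each reclassified subject moves the success rate by 1.0 percentage point in the convergent arm (1/102) or 2.0 points in the control arm (1/51).

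**Working it through.** **1. End of blanking under each document.** Let V be the number of days from the procedure to the 3-month visit.

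- Window (Protocol 6.4): 90 − 15 = 75 to 90 + 15 = 105.
- Protocol 6.1: end = V.
- SAP 7.4.2: end = V if 75 ≤ V ≤ 105; otherwise 90, if no other visit is in the window.
- Days blanked by the Protocol but counted by the SAP, visit day included, when V > 105: V − 90.

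| V | Protocol end | SAP end | Days exposed |
|---|---|---|---|
| 104 | 104 | 104 | 0 |
| 105 | 105 | 105 | 0 |
| 106 | 106 | 90 | 16 |
| 110 | 110 | 90 | 20 |
| 120 | 120 | 90 | 30 |
| 127 | 127 | 90 | 37 |

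The last row is the latest visit that Protocol 12.5 would still code to month 3 if closest means the nearest window edge. The month 6 window opens at 180 − 30 = 150, and (105 + 150)/2 = 127.5. Protocol 12.5 does not define closest, so this limit is an assumption.

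**2. Which data are caught.**

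- Cardioversion, and new or increased AAD use: placed by their own dates (SAP 7.4.5). They count from day 91.
- The late visit's ECG: counted under SAP 7.4.2 and 7.4.5, which go by the ECG date; not counted under the first statement in SAP 7.3. Unresolved.
- The late visit's Rhythm Disturbance form: SAP 7.4.2 says forms "which do not have a specific date on the CRF page will be assigned the date for that study visit". A symptomatic episode from before day 90, reported at a late visit, could therefore be dated after blanking. The same conflict with SAP 7.3 applies.

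**3. The plan's sample size.** Inputs from Protocol 9.2: 40% against 65%, two-sided alpha 0.05, 80% power, 2:1 allocation, 10% dropout. Pooled rate = (2 × 0.65 + 0.40)/3 = 0.567.

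n(control) = [1.96 × √(0.567 × 0.433 × 1.5) + 0.842 × √(0.40 × 0.60 + 0.65 × 0.35/2)]² / 0.25² = 45.7, rounded up to 46.

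Total 46 + 92 = 138, and 138/0.9 = 153.3. The stated 153 is reproduced.

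**4. Size under assumed rates.** The documents give neither the share of late visits nor the share of late visitors' successes that would be converted to failures. Assume 5% to 15% and 10% to 40%, equal in both arms. The share of successes lost, m, is then 0.05 × 0.10 = 0.5% to 0.15 × 0.40 = 6%. Success rates become 0.65(1 − m) and 0.40(1 − m). Exact power of the chi-square test in favour of the convergent arm:

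| m | Rates | Power at 102:51 | Power at 92:46 |
|---|---|---|---|
| 0 | 65.0% vs 40.0% | 84.0% | 80.2% |
| 0.5% | 64.7% vs 39.8% | 83.5% | 79.7% |
| 6% | 61.1% vs 37.6% | 78.3% | 74.3% |

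Expected successes lost at 102:51 are 102 × 0.65 × m = 0.3 to 4.0 in the convergent arm and 51 × 0.40 × m = 0.1 to 1.2 in control.

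**The case against.** **Protocol 6.1 may not cover a visit outside the window.** Protocol 6.4 defines the visit as 90 ± 15 days, and the endpoint text speaks of a 3-month blanking period. On that reading the SAP only supplies a default where the Protocol is silent. This has some force, but Protocol 12.5 keeps a late visit in the nearest slot. That section concerns coding and deviations rather than blanking, so it weakens the reading without closing it. On either reading, the step from 105 back to 90 has no stated reason.

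**Timing dependence is the Protocol's own design.** Visits in the window already give anything from 75 to 105 blanked days. True, but there the period grows with the visit date. Only the SAP default shortens it after the fact.

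A reader might also infer three stronger things that the documents do not support.

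- *That AF on the late visit's ECG is a failure.* SAP 7.4.2 and 7.4.5 point that way, but SAP 7.3 excludes out-of-window visits before reassigning unscheduled ones. The text does not settle it.
- *That every late visitor cardioverted after day 90 fails.* The default needs an empty window. A cardioversion at 98 days may itself produce an unscheduled visit. SAP 7.4.2 provides for this only "If the nominal 3 month visit is not performed but an unscheduled visit falls within that visit window", and does not say what happens if the nominal visit was also performed late.
- *That the rule favours one arm.* It is prespecified and identical in both. Differential lateness is possible in an open-label trial, but nothing in the documents shows it.

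**Conclusion.** The point holds for dated treatment events. With a 3-month visit later than 105 days and no other visit in the window, SAP 7.4.2 exposes at least 16 days that Protocol 6.1 blanks, and SAP 13 does not say so. The status of the late visit's own ECG and undated forms is a conflict within the SAP, not a settled rule.

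The expected effect is added failures in both arms and some loss of power. It is negligible at the low end of the assumed range. At the high end, power falls to 78.3% at 102:51, or 74.3% after the planned dropout. Those figures rest on assumed rates and on equal loss in both arms. The 40% upper rate has no support in the documents, since it concerns subjects with an event soon after day 90 and no other failure through month 12.

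This should be corrected before database lock, because it decides individual primary outcomes and is easy to remove.

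**What to change.** 1. In SAP 7.4.2, replace the default with wording such as: *If the 3-month visit is performed more than 105 days after the study procedure and no other visit falls within the window, the blanking period ends on the 105th day after the study procedure (upper limit of the window). If no 3-month visit takes place, it ends on the 90th day after the study procedure.* Count days from the procedure, as here, because study day 105 is only 104 days after it. The present sentence also covers a visit earlier than 75 days, so say that the 90-day default still applies there. Say too which visit governs when an unscheduled visit is in the window and the nominal visit is late.
2. Reconcile SAP 7.3 with 7.4.2 and 7.4.5, so that one rule covers ECGs and undated Rhythm Disturbance forms from an out-of-window 3-month visit. Do not exempt late-visit findings without a time limit. Otherwise AF on that visit's ECG at 125 days would be ignored, while AF at another contact at 107 days would count.
3. List in SAP 13 what still differs from Protocol 6.1 and 12.5: the time from the 106th day to the late visit (1 day for a visit at 106 days, 127 − 105 = 22 days for one at 127).

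The cost is SAP wording only. Late visitors gain up to 15 blanked days (91 to 105), which brings them to the maximum that in-window visitors already have.
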